Respiratory sinus arrhythmia is a direct measure of this vagal tone³¹ and is derived from HRV across the respiratory cycle. Heart rate variability is defined as the variation between consecutive heartbeats³³ or beat to beat variability³². It is considered a validated physiological mechanism for evaluating the state of the ANS and more specifically emotional responsivity. In a systematic review, Kirizawa and colleagues²⁹ have advocated for the use of HRV as a physiological marker to evaluate ANS function in individuals with leukemia. The heart's ability to demonstrate high variability is considered advantageous, but often undesirable intrinsic and extrinsic factors decrease variability. One such factor is the treatment of HCT in children with hematopoietic disease. Because RSA/vagal tone/HRV has been successfully used to investigate the ANS in pediatric traumatic brain injury³⁴, premature babies³⁵, and children with autism spectrum disorders^{36,37}, we believe its use with children undergoing HCT in our study is promising. An additional advantage is the fact that the collection of RSA/HRV is non-invasive and improved technological development has led to the delivery of reliable, portable HRV monitors. Again, making its use appealing with children undergoing HCT.

Motivation 2: Exploring the effect AT media on RSA/HRV, emotional state, and the health outcome of mobility in children undergoing HCT.

Recognizing that AT and certain aspects of AT media have promoted changes in the ANS as measured by HRV in children and adults³, and that calls have been made for the use of HRV in studies exploring AT interventions^{5,9,10}, we arrive at our second research motivation: to capture RSA/HRV during AT interventions in order determine if one type of media leads to improved changes in the ANS as captured by HRV/RSA, emotional ratings, and daily mobility.

Understanding the relationship between patient, therapist, and the art making material is critical to generate effective patient outcomes. Much of the AT evidence discusses the important bond developed

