As has been encouraged by AT literature and organizations, several studies have examined the impact of media. The first study looked at media's impact on the outcome of emotional responses and the second on HRV. Pesso-Aviv and colleagues explored the effects of pencils, oil chalks, and gouache paint on anxiety and self-control using survey data on 41 males between the ages of 7 to 9 years, who although not reported within the narrative appear to have been healthy, typically developing youth. Ten intervention session were provided for each of the three different media groups. Surprisingly, the results indicated no change in anxiety and self-control outcomes. This may be possibly explained by the youth being healthy and typically developing with little to no impairments in anxiety and self-control, thus, creating a ceiling effect with little space for documenting improvement. For children undergoing HCT, we know that emotional engagement and anxiety are problematic so media's impact may be more detectable in this group. In the second study, Haiblum-Itskovitch and researchers hypothesized that emotional and ANS responses as measured by RSA/HRV values would be more reflective of PNS activity as fluidity of the media decreases in a normative sample of adult participants; thus, pencils would offer the greatest PNS activity followed by oil pastel and then gouache with brush. Surprisingly, results indicated that oil pastels resulted in the greater PNS activation than gouache while also corresponded to more meaningful emotional engagement. Thirty-five percent of the variance in the PNS value was explained by the media with a change in the RSA value of 1 representing the effect size needed for detecting a meaningful difference between materials. The author offered the possibility that the oil pastels facilitated greater tactile input which like fluidity may also played a role in ANS activity and emotional engagement. Based on the above information and considering that no study has explored the use of RSA/HRV as a physiological measure by which to evaluate a media's impact on a population of children with a health

condition, our proposed study seeks to accomplish this by evaluating 2 media's impact on physiological (RSA/HRV), emotional (SAM), and health outcomes (mobility) of in children undergoing HCT.

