3.0 Intervention to be studied (if applicable)

Side-by-side integration of AT and PT has not been examined and we propose to conduct a clinical trial in which for two weeks daily (Monday-Friday), 20 children between the ages of 3-18 years will be randomly assigned into one of two groups: 1) collaborative intervention: 45 minutes of AT immediately followed by 30 minutes of PT or 2) PT only intervention: 30 minutes. During the collaborative intervention of week 1, oil pastels will be the media and week 2 gouache painting without brush.

Treatment: 45 minutes of AT closely followed by 30 minutes of PT OR 30 minutes of PT.

AT treatments will seek to reduce sympathetic dominance/physiological and emotional distress. Oil pastels will be used for Days 1-5 and gouache painting for days 6-10. Art therapy is a collaborative, interactive, and iterative process that evolves across the session between the child and art therapist, as such, outside of the actual change in medium, there is no study specific art therapy prescription or protocol. Art therapy sessions will occur in the child's room.

PT treatments will seek to prevent physical deconditioning and encourage mobility, ambulation, and selfcare participation based on participant's ability. Physical therapy sessions will occur in the child's room and on the HCT unit.

The same art and physical therapist and art therapist will conduct children's session across the 2-week study duration. This art and physical therapist commonly work on the HCT unit. The coordinator again will monitor all sessions to ensure the following of study procedures.

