4.0 Study Endpoints (if applicable)

Aim 1: Pre and post-test data collection, storage, and scoring calculations will be carried on by study coordinator/PhD student.

Pediatric Evaluation of Disability Computerized Adaptive Test (PEDI CAT) using a study iPad: The PEDI CAT measures 0 to 18-year-old children's abilities across three domains of mobility, selfcare and social function. It can be used with all pediatric diagnosis, across settings, and measures change following an intervention. It demonstrates excellent reliability⁴⁸, good validity^{49,50} with a minimal detectable change ranging between 2.2 to 3.3 across domains.⁵¹ Our study will measure only selfcare and mobility domains, which takes approximately 20 minutes to administer. Scaled (criteria referenced) and Standard (normative referenced) PEDI-CAT scores will be calculated.

6-Minute Walk Test (6MWT)

The 6MWT has demonstrated good reliability and validity in various pediatric populations.^{52,53} It has also been found to be predictive of cardiovascular fitness in survivors of children with pediatric cancers.⁵⁴ The 6MWT takes 6 minutes to administer.

Aim 2: Daily data collection by art and physical therapists during or after sessions, but data will be managed by study coordinator/PhD student following the sessions.

The Self-Assessment Manikin (SAM): The SAM is an image-based tool used to evaluate affective change in pleasure, arousal, and dominance in response to an object or event.⁵⁵⁻⁵⁷ (Appendix 6) Good reliability and validity of the SAM has been demonstrated.⁵⁸ Suggestions are that it perform similarly across diverse cultures and ages.⁵⁹⁻⁶¹ The SAM has been collected in studies involving exercise in which large

effect sizes were noted.⁶² We plan to use the computerized application of the SAM, which will take seconds to administer before and after daily AT and PT interventions.

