Respiratory Sinus Arrhythmia derived from Heart Rate Variability: HRV measures short-term R-to-R intervals, which is reflective of the autonomic nervous system. The portable, non-invasive Firstbeat Bodyguard 2 (Appendix 7) will be worn to gather HRV. The monitor will be placed on the chest of the child 10 minutes prior to the beginning of AT and worn by the child until removal following PT. We will evaluate the first and last 5-minute of HRV data during the AT session. Using Cardio Batch software, RSA will be calculated from the HRV data. The Firstbeat Bodyguard 2 accurately measures 99.95% of the heartbeats compared to standard EKG.⁶³ Placement and removal of the HRV monitor requires only seconds. The study coordinator/PhD student will clean all HRV files for artifact and calculate RSA values using Cardio Batch software. At the end of each day, the coordinator/PhD student will be responsible for collecting, cleaning, scoring, and storing all daily data.

Aim 3: Daily collection: Daily data collection by art and physical therapists during or after sessions, but data will be managed by study coordinator/PhD following the sessions.

Walking distance during PT session as measured by accelerometer: The ActiGraph GT9X Link (Appendix 8) will collect walking distance as measures by distance and steps during PT. It is similar in looks and wear to an iWatch. It has demonstrated good reliability and validity.^{64,65} It can collect a variety of outcomes (e.g., energy expenditure, body position, sleep), but for aim 3, we will be most interested in walking distance and number of steps. At the end of each day, the study coordinator/PhD student will be responsible for collecting, calculating distance and step values using Actigraphy software, and storing accelerometry data.

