Aim 2: Do children receiving PT plus AT have physiological (sympathetic or parasympathetic) and emotional responses to oil pastels and gouache as measured by respiratory sinus arrhythmia derived from heart rate variability and Self-Assessment Manikin scores during each of the daily AT sessions.

Hypothesis 2: Oil pastels or gouache AT will generate a RSA value in the direction of needed parasympathetic activity and balance the emotions of valence, arousal, and dominance.

Statistical Test: Repeated measures generalized linear regression

Aim 3: In children receiving PT plus AT, determine if there is a stronger association between the RSA values of oil pastels or gouache AT and an increased walking distance as measured by accelerometry during daily PT sessions.

Hypothesis 3: The media that best generates a parasympathetic RSA value and emotional balance will be associated with a greater walking distance.

Statistical Test: Repeated measures generalized linear regression

Data Collection

The 10-day intervention will begin on approximately Day 15 of HCT. Pre-test (Pediatric Evaluation of Disability Inventory and 6-Minute Walk Test) will be collected on Day 14. The same post-test data will be collected the day following the tenth day of intervention.

During the 10 days of intervention, the Self Assessment Manikin, heart rate variability, and walking distance will be collected daily.

The study coordinator will be responsible for storing all data. All documentation and data concerning each participant will be coded to protect confidentiality. All data collection and storage processes and locations will use study equipment (i.e., heart rate variability monitors, computers, College of Health Professions DA server) that is password protected, encrypted, and behind the MUSC firewall. All study related equipment will be locked in the office of the PI when not in use. There will be no transfer of data to a third party.

Procedures

- 1) IRB approval
- 2) Begin participant enrollment
- 3) Collaborate with HCT team to initiate recruitment and share study flyer
- 4) PI will obtain informed consent from participants in the hospital or electronically through MUSC secure email.
- 5) Randomize participant to AT and PT or PT only
- 6) Approximately Day 14 of HCT complete pre-test (Pediatric Evaluation of Disabilities Inventory and 6-Minute Walk Test)

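### Both RSA windows lie inside the art therapy session, the pre-session recording has no stated use, and the RSA contrast is undefined

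*Combined protocol and SAP*

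**What the plan says.** Under Aim 2, section 4.0 starts the heart rate variability (HRV) recording before the session: "The monitor will be placed on the chest of the child 10 minutes prior to the beginning of AT". The device stays on until physical therapy has ended. The windows to be analysed are then named: "We will evaluate the first and last 5-minute of HRV data during the AT session". Section 3.0 sets the combined session as "45 minutes of AT immediately followed by 30 minutes of PT", so the two windows cover 10 of the 45 AT minutes, and both fall within AT. No section gives the 10 earlier minutes a role in an analysis, and none says they are only for settling.

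Motivation 2 in section 2.0 gives the purpose: "to capture RSA/HRV during AT interventions in order determine if one type of media leads to improved changes in the ANS". The other Aim 2 outcome, the Self-Assessment Manikin (SAM), is described in section 4.0 as a tool "which will take seconds to administer before and after daily AT and PT interventions". SAM therefore has a value from before the session, and RSA has none that is planned for use.

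In section 10.0, Data Analyses, the whole stated method for Aims 2 and 3 is "Repeated measures generalized linear regression". The form of the RSA outcome, the contrast and the covariates are not given. On what happens within a session, section 3.0 says that "outside of the actual change in medium, there is no study specific art therapy prescription or protocol".

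**The concern.** Aim 2 asks how the child's autonomic state responds to each medium. A response needs a reference, and the only early RSA value the plan names comes from inside the exposure. If the child handles the medium soon after the session starts, that reference may already hold part of the response. Subtracting it would shrink the response, and would distort the comparison if the two media act at different speeds.

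If the plan instead intends the last-window level with no reference, the child's condition on arrival that day (fever, sleep, a procedure) goes unadjusted. With 10 children in the arm that receives AT, precision matters.

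A value certain to precede AT should be obtainable from a recording the trial already makes.

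**Working it through.** **The plan's own figure.** The only numbers tied to the RSA endpoint are the 61 and 82 measurement points for 80% and 90% power (section 10.0, Power). They do not depend on the choice of window. Section 10.0 gives no numeric effect size or standard deviation. With a two-sided alpha of 0.05 (the plan does not state sidedness), the conventional medium values tried do not give both figures:

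- two-sample t, d = 0.5: 64 and 86 per group
- paired t, d = 0.5: 34 and 44
- regression, f² = 0.15: 55 and 73 with one predictor, 68 and 88 with two
- correlation, r = 0.30: 85 and 113

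A correlation of 0.35 fits (power 0.8015 at 61 and 0.9046 at 82), but that value is not in the power section. I therefore attach no power loss to this point.

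**Inputs.** Two 5-minute windows inside AT and 10 minutes of wear before AT (section 4.0); 10 children with 10 sessions each, or 100 sessions (section 10.0). For scale only, section 2.0 reports from a cited study of a normative adult sample "a change in the RSA value of 1 representing the effect size needed for detecting a meaningful difference between materials". The documents give neither f, the share of the full pre-AT-to-end response already present in the first 5 minutes, nor rho, the session-level correlation between the reference and last-window RSA. Both are assumptions.

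**Reading A: last minus first window.** Observed change = (1 - f) × true change. For a true change of 1 unit:

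| f | observed change |
|---|---|
| 0 | 1.00 |
| 0.10 | 0.90 |
| 0.25 | 0.75 |
| 0.50 | 0.50 |
| 0.75 | 0.25 |

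If f differs by medium, the comparison is biased as well. With equal true changes of 1 and f of 0.25 and 0.50, the observed changes are 0.75 and 0.50, a spurious difference of 0.25.

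**Reading B: last window adjusted for first window.** With covariate slope b and the same f for both media, the media effect kept is 1 - b × f. At b = 0.5 and f = 0.50 this is 1 - 0.25 = 0.75. The loss is smaller than in Reading A, but the covariate is still possibly exposed.

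**Reading C: last-window level alone.** The full effect is kept and f plays no part. The session variance (set to 1) includes all of the pre-session state.

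**Gain from a pre-AT covariate.** Take equal variances and the same rho for whichever reference is used:

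- adjusted level: variance 1 - rho²
- unadjusted level: variance 1
- change score: variance 2(1 - rho)

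| rho | adjusted level | unadjusted level | reduction | change score | reduction |
|---|---|---|---|---|---|
| 0.5 | 0.75 | 1.00 | 25% | 1.00 | 25% |
| 0.7 | 0.51 | 1.00 | 49% | 0.60 | 15% |

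The last column is 1 - 0.51/0.60 = 0.15. Loss of effect arises when the first window is the reference. The full pre-session noise arises only in Reading C. The two do not occur together at these sizes.

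**The case against.** The strongest reply is that the plan does what its aims say. The Specific Aims ask about responses during the daily AT sessions, and measuring inside the session contradicts nothing. That stands: a pre-AT reference is an improvement, and its absence is not an inconsistency.

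Other parts of the reply also stand, and they rule out stronger readings that a reader might infer:

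- **That RSA is measured only at the start of AT, or that the plan uses a change score.** The last 5 minutes are evaluated too, and neither section 4.0 nor section 10.0 defines a last-minus-first outcome.
- **That the child is already using the medium in the first window.** The documents do not say when the medium is first handled. With no set session content, AT could open with talk or set-up, and f could be near 0. The same lack of a set content means that exposure in that window is uncontrolled.
- **That a planned 1-unit difference is being halved.** The value of 1 comes from the cited adult study. The plan's power statement names only a medium effect, and the documents do not show what reference that study used.
- **That the pre-AT recording is a ready resting baseline.** The minutes may serve for settling after placement, and the pre-session SAM may fall within them. Posture and movement may also differ from the AT windows.

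For Aim 3, the question is how RSA values relate to walking distance. Adding pre-AT RSA turns this into an association with RSA given the starting state, which is a different quantity.

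**Conclusion.** The point holds as a low-cost improvement in precision and protection. Both RSA windows lie inside AT, no use is stated for the 10 minutes recorded beforehand, and the analysis section leaves open whether RSA is a level or a change. Loss of effect is possible but not shown. It runs from none at f = 0 to three quarters at f = 0.75 if the first window is subtracted, and is nil if the last-window level is analysed alone. In that second case the cost is unadjusted pre-session noise.

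The gain from a pre-AT covariate is 25% to 49% of variance against an unadjusted level for rho of 0.5 to 0.7. Against a change score it is 25% falling to about 15%. These figures rest on assumed rho, equal variances and equal correlation for the two references.

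The change would not separate medium from week. Section 3.0 gives oil pastels on Days 1-5 and gouache on Days 6-10, and a session baseline does not remove that confounding.

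**What to change.** 1. In sections 4.0 and 10.0, define the RSA outcome and contrast for Aim 2.
2. Compute RSA for the last 5 of the 10 pre-AT minutes in every AT session. Record posture and activity in that interval, and whether SAM was given during it.
3. As the main Aim 2 analysis, model last-5-minute RSA by medium in the planned repeated measures regression, with that session's pre-AT RSA as covariate. Keep the first window, and report first-to-last change as supportive.
4. For Aim 3, keep the association as planned and show the pre-AT-adjusted model only as a sensitivity analysis, saying that it estimates a different association.
5. If the sponsor prefers the in-session reference, state why, and state what the pre-AT recording is for.

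The cost is one more 5-minute segment to clean per session: up to 100 segments for 10 children over 10 sessions, on top of the 200 already planned (2 × 100). No new procedure is needed. The drawback is that posture, movement or settling before AT may differ from the AT windows, which is why the value enters as a covariate and not as the sole comparator.

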5.0 Inclusion and Exclusion Criteria/ Study Population

Inclusion criteria: Children between the ages of 4 and 18 years undergoing HCT in response to hematological disease during the in-patient hospital treatment phase.

Exclusion criteria: Children with central nervous system impairments (e.g., cerebral palsy), other genetic diseases (e.g., Down syndrome), and cognitive impairment will be excluded from study participation.

Children undergoing HCT were chosen as this study's population because they often receive intermittent and stand-alone AT or PT. We believe more daily PT and/or AT as well as the collaboration between PT and AT will improve health outcomes. Because children display continual cognitive, behavior, and motor development changes, this study chose not to involve adults undergoing HCT. The outcomes for children and adults undergoing HCT cannot be validly compared. This study has no exclusions for any specific sex/gender or racial/ethnic group.

6.0 Number of Subjects

20

Approximately 30 children undergo HCT at MUSC Children's Hospital annually for which 50% are male and female, 10% considered Hispanic, 55% Caucasian, and 35% African American.

7.0 Setting

MUSC Shawn Jenkins Children's Hospital.

8.0 Recruitment Methods

Participants will be recruited prior to and at the time of admission for the HCT. A flyer will be provided to the HCT team members to share with participants. Members of the HCT team will be made aware of the inclusion criteria and can approach all potential participants for possible study enrollment. While any team member may recruit a study participant, the study art therapist and physical therapist, who commonly associated with the HCT team, will especially be important for recruitment. In the majority of cases, they are aware of dates that children will be transiting into the hospital for HCT. The study art therapist and physical therapist have a developed relation with the study PI. The art therapist and PI serve together as leaders within the MUSC Office of Humanities. The art therapist has also provided instruction within the PIs' DPT and IP courses. The physical therapist is a graduate of the DPT program in which that the PI teaches. The physical therapist and PI have carried out national presentations together and the physical therapist also instructs within the PI's courses. Participants and HCT team members will contact the PI when interest in enrollment is expressed. Parents will be welcome to contact the PI as well. The PI will contact parents of participants and seek informed consent and assent for study participation.

9.0 Consent Process

Informed consent will be sought upon each child's admission to MUSC Shawn Jenkins Children's Hospital. It will occur approximately on or before Day 13 of the HCT. Day 14 will be for pre-testing and day 15 for start of intervention. Children's authorized representative will have at least 24 hours prior to study intervention initiation.

Consent may be obtained in person at the hospital or using an electronic consent.

For in person consents, the PI will obtain informed consent from parents or legal guardians at the MUSC Shawn Jenkins Children's Hospital.

The PI will communicate by phone or email with the parent or legal guardian to establish a time to seek informed consent at the hospital OR discuss the use of an electronic consent. If an electronic consent is used, the PI will email the consent to the parent or legal guardian using secure MUSC email. Then the PI will contact the parent or legal guardian by phone to review the informed consent and answer any questions. If the parent or legal guardian wishes to enroll in the study, they will sign the informed consent and return to the PI through the MUSC email system.

Assent will be obtained from each individual child or adolescent at the same time that the informed consent is obtained from parents. If informed consent is carried out electronically, the parent will be asked to document the child or adolescent's assent using MUSC email communication.

If a child withdraws assent prior to a study session, parents will be notified. If the child withdraws assent for a session for 3 days in a row, the child will be withdrawn from the study. If assent is less than 3 days, then missed days will be added to the study duration until 10 days are completed.

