10.0 Study Design / Methods

Design: Randomized clinical trial to compare collaborative AT and PT to only PT in children undergoing HCT.

Using excel, the study coordinator will randomize each participant to either the PT and AT or PT only group. Each group will be assigned 10 participants.

Power

With a recruitment expectation of 30 participants, we expect a 30% drop out rate leaving 20 enrolled participants and feel confident that this study's aim 2 and 3 will be successfully powered to identify statistical significance ($p<0.05$) in outcomes. For Aims 2 and 3 which involve the collection of clustered data for HRV, SAM, and walking distance, in order to identify a medium effect, 80% or 90% power will be achieved with 61 or 82 measurement points respectively.^{54,55,66,67} Accounting for a dropout rate of 30%, the expected number of participants is 20. With 10 participants in the intervention group, 100 measurement points for HRV, SAM, and walking distance each are expected; thus, ensuring adequate power for aim 2 and 3.

For the PEDI CAT and 6MWT, to achieve 80% power, the projected sample size in each group is estimated to be 16 and 20; therefore, we proposed that we may not be adequately powered for aim 1.^{51,68} However, findings attributed to aim 1 will provide pilot data to inform a larger randomized control trial. Although aim 1 may not be adequately powered, the published minimal detectable change (MDC) for the PEDI CAT selfcare and mobility domains are 2.2 and 2.5 respectively while the Minimally Clinically Important Difference (MCID) for the 6MWT is 7%.^{69,70} Although, power to find a statistically significant difference may be inadequate, we expect to observe this level/magnitude of improvement in our proposed study. Variation values from this aim will provide data that are essential to guide future research.

Data Analyses

Aim 1: In children undergoing HCT during in-patient care, do a randomized group receiving a combination of Physical Therapy (PT) plus Art Therapy (AT) have improved functional activity level outcomes of self care and mobility as measured by the Pediatric Evaluation of Disability Inventory Computerized Adaptive Test and the 6-Minute Walk Test, compared with a group receiving PT only.

Hypothesis 1: Children receiving the combined intervention of PT plus AT will demonstrate greater improvements in self care and mobility skills.

Statistical Test: Independent sample t-tests

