- 7) Day 15-24 of HCT: 45 minutes of AT and 30 minutes of PT OR 30 minutes of PT only. Heart rate variability, Self Assessment Manikin, accelerometry collected across sessions.
- 8) Approximately Day 25 of HCT complete post-test (Pediatric Evaluation of Disabilities Inventory and 6-Minute Walk Test)
- 9) Data analyses and dissemination.

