12.0 Data Management

All documentation and data concerning each participant will be coded to protect confidentiality. All data collection and storage processes and locations will use study equipment (i.e., heart rate variability monitors, computers, College of Health Professions DA server) that is password protected, encrypted, and behind the MUSC firewall. All study related equipment will be locked in the office of the PI when not in use. There will be no transfer of data to a third party.

13.0 Provisions to Monitor the Data to Ensure the Safety of Subjects (if applicable)

All documentation and data concerning each participant will be coded to protect confidentiality. All data collection and storage processes and locations will use study equipment (i.e., heart rate variability monitors, computers, College of Health professions DA server) that is password protected, encrypted, and behind the MUSC firewall. All study related equipment will be locked in the office of the PI when not in use. There will be no transfer of data to a third party.

Children undergoing HCT will experience symptoms related to the HCT and may experience additional medical complications. Our study involving art and physical therapy interventions will only be carried out during the in-patient phase, which will be helpful when considering adverse effects because a variety of

healthcare professionals will be at hand to possibly prevent and ameliorate any adverse events. For example, prior to each daily session, the art and/or physical therapist will ask the child's nurse if the patient is medical stable to participate. If the nurse, reports that the child is not medically stable, then the child's session will be postponed until stable.

Common symptoms following transplant include fatigue and deconditioning which is associated with lower strength and endurance. We believe children' participation in this study will lead to temporary reports of elevations in fatigue, weakness, and poorer endurance symptoms; however, we will not view these as adverse events since these symptoms are also common to increases in activity level that will be generated by art and physical therapy.

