14.0 Withdrawal of Subjects (if applicable)

Not applicable.

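### Three straight days of refusal withdraw a child from the study, not only from the intervention, and no post-test is described for that child, so Aim 1 probably loses randomised children who refused their assigned treatment

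*Combined protocol and SAP*

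**What the plan says.** The refusal rule is in section 9.0: "If the child withdraws assent for a session for 3 days in a row, the child will be withdrawn from the study". The sentence before it, on notifying parents, begins "If a child withdraws assent prior to a study session". The sentence after it says that days missed through shorter refusals are added until ten are completed. A child who refuses for one or two days therefore stays in and reaches the post-test.

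Section 14.0 is the place for withdrawal rules, and it is marked as not applicable. By contrast, section 13.0 says that discharge home stops the study intervention; it does not call this withdrawal from the study.

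On the post-test, section 10.0 (Data Collection) says "The same post-test data will be collected the day following the tenth day of intervention", and the Procedures list in the same section says "Approximately Day 25 of HCT complete post-test". Randomisation is step 5 of that list and the pre-test is step 6, so a refusal during the intervention always falls after randomisation.

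The whole Aim 1 analysis is "Statistical Test: Independent sample t-tests". No analysis set and no method for missing data are given. Section 10.0 assigns 10 children to each group. Section 3.0 gives the combined arm "45 minutes of AT immediately followed by 30 minutes of PT" and the other arm 30 minutes of PT.

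**The concern.** Aims 2 and 3 are analysed within the combined arm only, so randomisation protects Aim 1 alone. Under the refusal rule, whether a child has an Aim 1 outcome depends on whether the child accepted the assigned treatment. The two arms ask for different things: 45 + 30 = 75 minutes a day against 30. Children who refuse for three days running may therefore differ between arms, and they may do better or worse than those who stay. If they drop out of the comparison, the children left in the two arms may no longer be comparable.

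The plan already concedes that Aim 1 may be underpowered and calls it pilot data for a larger trial. That concession covers low power but not selective loss. A pilot estimate carried into the design of the next trial should be as free of this as can cheaply be arranged, and a post-test not collected at the time cannot be recovered. The rule may also give up outcome data from children who would refuse more sessions but still agree to be tested.

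**Working it through.** **1. Does following the text lose the child?** There are four steps.
- Section 9.0 ends study participation after three straight days of refusal.
- Section 10.0 (Data Collection) ties the post-test to the tenth intervention day, which a withdrawn child does not reach. The Procedures list gives an approximate day, but nothing extends it to a withdrawn child.
- Section 14.0 supplies no follow-up rule.
- A t-test, whether on the post-test or on change, needs a post-test value.

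The loss is thus an inference from these parts together; no sentence states it.

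**2. The plan's own dropout figure (section 10.0, Power).** The plan expects 30 recruited, 30% dropout and 20 remaining. Forward: 30 × (1 − 0.30) = 21, against the stated 20. Backward: 20 / 0.70 = 28.6, rounded up to 29, against the stated 30. The figure reproduces to within rounding. The 20, and hence the 10 per arm, is already net of the 30%.

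**3. Precision.** In units of the outcome SD (equal SDs assumed), the 95% half-width for a difference in means is t(0.975, n1 + n2 − 2) × √(1/n1 + 1/n2). The number lost is an assumption; the documents give none.

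| Arm sizes | t | √(1/n1 + 1/n2) | Half-width (SD) |
|---|---|---|---|
| 10 vs 10 | 2.101 | 0.447 | 0.94 |
| 10 vs 9 | 2.110 | 0.459 | 0.97 |
| 10 vs 8 | 2.120 | 0.474 | 1.01 |
| 10 vs 7 | 2.131 | 0.493 | 1.05 |

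**4. Power.** Section 10.0 gives 16 and 20 per group for 80% power, without effect sizes. Solving back (two-sided 0.05 assumed) gives standardised differences of 1.02 and 0.91. Power at 10 vs 10 is then about 58% and 49%; at 10 vs 9 it is about 56% and 46%. One loss costs 2 to 3 percentage points.

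**5. Possible shift in an arm mean.** If k of 10 children are lost, the retained mean differs from the full-arm mean by (k/10) × (retained mean − lost mean). The documents do not give that gap. As a yardstick only, set it to the PEDI CAT minimal detectable change in section 10.0, which is 2.2 for self-care and 2.5 for mobility:
- k = 1: 0.22 and 0.25 points
- k = 2: 0.44 and 0.50 points
- k = 3: 0.66 and 0.75 points

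The bias in the arm difference is the shift in one arm minus the shift in the other. Equal losses with equal gaps would cancel.

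**The case against.** The strongest reply is that the loss is read from silence. The rule sits in the consent section and protects a child who keeps dissenting; it does not define an analysis set. Nothing forbids a post-test, and the Procedures list could be read as a calendar visit. This stands in part: the plan does not say that such children are excluded from Aim 1, and a reader should not report that it does. But staff who follow the text have no instruction to test a child who has left the study.

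The effect may also be slight. Short refusals are handled by make-up days, one loss barely changes precision, and Aim 1 is declared pilot work. All of that stands and limits the severity.

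Two stronger readings are tempting and are not supported.

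- **Three of ten lost per arm.** A reader might apply the 30% dropout to the 10 per arm. That counts the dropout twice, since 20 is what remains after it. Nor does the plan link the 30% to three-day refusal.
- **Withdrawal for declining art therapy alone.** Because the combined arm has two components and the rule does not define a session, a reader might infer that a child who declines only AT is withdrawn, while a PT-only child with the same PT attendance stays. The neighbouring sentences in 9.0 speak of a study session and of missed days, and section 13.0 has "prior to each daily session, the art and/or physical therapist will ask". These fit the whole daily visit better. The wording should still be tightened, but the built-in asymmetry is not established.

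**Conclusion.** The point holds as a minor to moderate weakness. As written, the plan withdraws persistent refusers from the study and describes no post-test for them. The likely result is that randomised children leave the only randomised comparison because they refused their assigned treatment. This rests on taking the withdrawal wording at face value and on no post-test being done by local custom.

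The number lost cannot be computed, nor can the size or direction of bias, and the documents do not show that either arm is favoured. For a single loss from 10 vs 10, the half-width moves from 0.94 to 0.97 SD. The mean shift would be 0.22 to 0.25 PEDI CAT points only if the lost child differed from the retained children by the minimal detectable change, which is an assumption. The case for acting is that avoidable selective loss can be prevented cheaply, not that the trial is shown to be biased.

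**What to change.** In section 9.0, with section 14.0 made consistent:

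- State that refusing the study visit on three consecutive days stops the study intervention, not study participation.
- Define a session identically in both arms, as the whole daily study visit.
- Ask the child's assent and the parent's agreement for the post-test separately, and respect a refusal.
- Offer the post-test to every randomised child at the planned time: about Day 25, or the day after the tenth session would have fallen, or before discharge if that is earlier.
- Analyse Aim 1 by assigned arm.

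One planned day should be chosen and written down, because the plan's timings do not quite agree. Ten Monday-to-Friday sessions (section 3.0) starting on Day 15 end on Day 26 if Day 15 is a Monday, and on Day 28 for any other weekday. The following day is then Day 27 or Day 29, not Day 25.

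Make-up days for shorter refusals, notice to parents and the daily nursing check stay as they are.

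The cost is a few sentences and one post-test of about 26 minutes per affected child (section 4.0: PEDI CAT about 20, 6MWT 6). Some children will be analysed with fewer than ten sessions. Their post-test will also fall at a slightly different time from that of children who used make-up days.
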